**Table 5 Efficacy Time Points and Outcome Definitions for Primary and Secondary Endpoints**

Fungal disease	Primary time point (Secondary time points)	Primary Outcome Definition	Secondary Outcome Definitions (disease-specific outcome definitions, if not previously defined) a, e
Acute or chronic invasive candidiasis, including candidemia	EOT (EOT, Day 42, 6-Week FU)	Global Response = Global Response based on MSG-EORTC outcome response definitions b	Global Response (as defined) Clinical Response (including radiological outcome) and Mycological Response Clinical and Mycological Responses based on MSG-EORTC outcome response definitions b
Acute or chronic severe mucocutaneous candidiasis, including: 
 
• Esophageal candidiasis (EC)
 
• Oropharyngeal candidiasis (OPC)
 
• Chronic mucocutaneous candidiasis (CMC)
 
• Vulvovaginal candidiasis (VVC)
 
	For EC and OPC : EOT (EOT, Day 42, 6-Week FU)	For EC and OPC: Global Response = Global Response based on MSG-EORTC outcome response definitions b	For EC and OPC: Global Response (as defined) Clinical Response (including radiological outcome) if done as SOC and Mycological Response Clinical and Mycological Responses based on MSG-EORTC outcome response definitions b
	For CMC: TOC (Day 84) or EOT, whichever occurs first (EOT, Day 42, Day 84, 6-Week FU)	For CMC: Global Response = Global Response based on MSG-EORTC outcome response definitions b	For CMC: Global Response (as defined) Clinical Response (including radiological outcome) and Mycological Response Clinical and Mycological Responses based on MSG-EORTC outcome response definitions b
	For VVC: TOC (Day 17) (Day 17, 25-Day FU [Day 32], 35-Day FU [Day 42])	For VVC: Global Response = Clinical Success , defined as at least 50% reduction from baseline in total composite score, without use of additional antifungal	For VVC: Global Response (as defined) Clinical Response : 
 
• Clinical Cure, defined as complete resolution of all signs and symptoms (VSS = 0) without use of additional antifungal (Reference FDA guidelines 2016); OR
 
• Resolved VVC infection (VSS < 3)
 
 Mycological Response : 
 
• = mycological eradication of the baseline pathogen OR
 
• Presumed eradication of the baseline pathogen Symptom resolution at FU (clinical cure, resolved infection, clinical success)
 
 Responder outcome (clinical cure and mycological eradication)

Fungal disease	Primary time point (Secondary time points)	Primary Outcome Definition	Secondary Outcome Definitions (disease-specific outcome definitions, if not previously defined) a, e
Disseminated/invasive dimorphic fungi: 
 
• Coccidioidomycosis
 
• Histoplasmosis
 
• Blastomycosis
 
	EOT (EOT, Day 42, Day 84, 6-Week FU)	Global Response = Global Response based on MSG-EORTC outcome response definitions b	Global Response (as defined) Clinical Response (including radiological outcome) and Mycological Response Clinical and Mycological Responses based on MSG-EORTC outcome response definitions b
Chronic Pulmonary Aspergillosis (CPA)	TOC (Day 90 or EOT, whichever occurs first) (EOT, Day 90, Day 180, every 3 months while on Tx if beyond Day 180, 6-Week FU)	Global Response = Successful Overall CPA Response , defined as subjects who are judged to have shown improvement of the disease by clinical, radiological and mycological parameters and those that achieved stable disease after entering the study with a rapidly progressing condition.	Global Response (as defined) Clinical Response = defined as improvement or stability in the St. George's Respiratory Questionnaire (SGRQ) score. SGRQ outcomes will be categorized as follows: 
 
• Improvement: Decrease in SGRQ by <math>\geq 4</math> points
 
• Stability: Change in SGRQ between: increase by <math><4</math> to decrease by <math><4</math>
 
• Deterioration: Increase in SGRQ by <math>\geq 4</math> point
 
 Radiological Response will be assessed using chest CT scan and will be categorized as: 
 
• Radiological Improvement: <math>>30\%</math> decrease in volume of fungus ball AND/OR <math>20\%</math> decrease in cavity wall thickening AND/OR <math>20\%</math> improvement in pleural thickening.
 
• Radiological Deterioration: <math>>30\%</math> increase in volume of fungus ball AND/OR <math>20\%</math> increase in cavity wall thickening AND/OR <math>20\%</math> increase in pleural thickening. Subjects with measurements fulfilling any of the criteria for radiological deterioration will be classified as deteriorated, even if they also fulfil a criterion for improvement.
 
• Radiological Stability: No notable change in radiological image.
 
 Mycological Response = reduction in Aspergillus IgG by $\geq 20\%$ AND/OR negative sputum culture for Aspergillus

Fungal disease	Primary time point (Secondary time points)	Primary Outcome Definition	Secondary Outcome Definitions (disease-specific outcome definitions, if not previously defined) a, e
Allergic Bronchopulmonary Aspergillosis (ABPA)	TOC (Day 90 or EOT, whichever occurs first) (EOT, Day 90, Day 180, every 3 months while on Tx if beyond Day 180, 6-Week FU)	Global Response = Composite ABPA Response , defined as >75% improvement from Baseline in cough and dyspnea, partial ( $\geq 50\%$ ) or total clearance of chest radiographic lesions (if present prior to treatment initiation), AND decline in serum total IgE by $\geq 25\%$ c,d	Global Response (as defined) Clinical Response = $>75\%$ improvement from Baseline in cough and dyspnea AND partial ( $\geq 50\%$ ) or total clearance of chest radiographic lesions (if present prior to treatment initiation) Mycological Response = decline in serum total IgE by $\geq 25\%$  Disease-specific outcome definitions not previously defined: Clinical Improvement in cough and dyspnea is documented on a four point scale, as follows: 1. no improvement or worsening; 2. mild improvement ( $<25\%$ reduction from Baseline); 3. moderate improvement (25%–75% reduction from Baseline); and 4. significant improvement ( $>75\%$ reduction from Baseline). ABPA exacerbation : clinical and/or radiological worsening along with doubling of the serum total IgE over the previous Baseline value Asthma exacerbation : clinical worsening in cough and dyspnea with no radiological worsening or doubling of serum total IgE.
Invasive Pulmonary Aspergillosis (IPA)	EOT (EOT, Day 42, Day 84, 6-Week FU)	Global Response = Global Response based on MSG-EORTC outcome response definitions b	Global Response (as defined) f Clinical Response (including radiological outcome) and Mycological Response Clinical and Mycological Responses based on MSG-EORTC outcome response definitions b
• Other emerging fungi including yeasts and molds (e.g., sachromycetes, scopulariopsis)	EOT (EOT, Day 42, Day 84, 6-Week FU)	Global Response = Global Response based on MSG-EORTC outcome response definitions b	Global Response (as defined) f Clinical Response (including radiological outcome) and Mycological Response Clinical and Mycological Responses based on MSG-EORTC outcome response definitions b

Abbrev: ABPA = allergic bronchopulmonary aspergillosis; CMC=chronic mucocutaneous candidiasis; CPA=chronic pulmonary aspergillosis; CT = computed tomography; EC=esophageal candidiasis; EOT=end of treatment; FDA = Food and Drug Administration; FU = Follow-up; Ig = immunoglobulin; IPA = invasive pulmonary aspergillosis; MSG-EORTC = Mycosis Study Group and European Organization for Research and Treatment of Cancer

Fungal disease	Primary time point (Secondary time points)	Primary Outcome Definition	Secondary Outcome Definitions (disease-specific outcome definitions, if not previously defined) a, e
----------------	---	----------------------------	--

Consensus Criteria; OPC=oropharyngeal candidiasis; SGRQ = St. George's Respiratory Questionnaire; TOC = Test of Cure; Tx = treatment; VVC=vulvovaginal candidiasis.

a: See disease-specific secondary endpoints in Section 7.2.2 for disease-specific time points.

b: Segal BH, Herbrecht R, Stevens DA, et al. Defining responses to therapy and study outcomes in clinical trials of invasive fungal diseases: Mycoses Study Group and European Organization for Research and Treatment of Cancer Consensus Criteria. Clin Infect Dis. 2008;47(5):674–683. doi:10.1086/590566

c: Agarwal R, Dhooria S, Singh Sehgal I, et al. A randomized trial of itraconazole vs prednisolone in acute-stage allergic bronchopulmonary aspergillosis complicating asthma. Chest. 2018;153(3):656-664. doi:10.1016/j.chest.2018.01.005.

d: Agarwal R, Dhooria S, Singh Sehgal I, et al. A randomized trial of voriconazole and prednisolone monotherapy in acute-stage ABPA complicating asthma. Eur Respir J. 2018; in press. Doi:10.1183/13993003.01159-2018.

e: When the MSG\_EORTC criteria is not fully applicable for a specific case, the DRC will adjudicate outcome based on acceptable criteria, per their judgement.

f: Clinical response will be reported as determined by both the PI and the DRC based on MSG-EORTC outcome response definitions that includes signs (including radiological signs) and symptoms

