14.2.2 Mycological Testing

14.2.2.1 Vulvovaginal Candidiasis

Samples for fungal culture will be collected at Screening, EOT (Day 7), TOC (Day 17 [± 3]) and 25-Day FU (25 days after EOT; 32 days after first dose). Additional samples will be obtained, if applicable, at Baseline/Day 1 and at any unscheduled visits. For symptomatic subjects, samples will also be collected at the 35-Day FU visit (35 days after EOT; 42 days after first dose).

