21.4 Appendix D: Vulvovaginal Signs and Symptoms Scale

SIGNS:

To be rated by the Investigator during the vulvovaginal examination

Sign	Absent 0	Mild 1	Moderate 2	Severe 3
Edema				
Erythema				
Excoriation or fissures				

Definitions:

Absent: none

Mild: slight

Moderate: definitely noticeable

Severe: marked, intense

SYMPTOMS:

To be rated by the subject

Symptom	Absent 0	Mild 1	Moderate 2	Severe 3
Burning				
Itching				
Irritation				

Definitions:

Absent: I have no discomfort (i.e., burning, itching, irritation)

Mild: I have some discomfort (i.e., burning, itching, irritation), but it does not bother me much

Moderate: I have discomfort (i.e., burning, itching, irritation), which is annoying, but not enough to affect what I am doing

Severe: I have discomfort (i.e., burning, itching, irritation), which is annoying enough to affect what I am doing

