**Table 4 Schedule of Treatment Visits and Study Procedures for VVC**

Study Visit/ Day	Screen a	BL/ Day 1 a	D4	EOT D7	TOC D17	25- DAY FU D32 b	35- DAY FU c D42	Unsc h Visits
Study Procedures	-1 (-3)	Prior to Tx		Phone/ On-site c	± 3 days		Phone/ On- site c	
GENERAL								
Informed Consent	X							
Subject Enrollment and ID Assignment	X							
Medical History and Demographics	X							
Inclusion/Exclusion Criteria	X	X						
Pregnancy Test	X							
Prior and Concomitant Medications	X----- X							X
Study Drug Dispensing		X						
Study Drug Collection and Review								
Subject Diary Dispensing and Collection		X			X			
EFFICACY								
Targeted PE including Clinical Evaluation of Signs and Symptoms of Infection	X	X		X	X	X	If applic. d	
Mycological Testing (fungal culture)	X	If applic. .		X	X	X	If applic. d	If applic. .
Assessment of Recurrence						X		
Subject Status (alive/ deceased)							X	
Assessment of Efficacy				X	X	X	X	
SAFETY								
Vital Signs	X	X		X				X
General Physical exam	X			X				
Clinical Laboratory Safety Assessments	X			X		X		If applic. .
Adverse events	X----- --X							
PHARMACOKINETIC								
PK Assessments e								

Study Visit/ Day	Screen a	BL/ Day 1 a	D4	EOT D7	TOC D17	25- DAY FU D32 b	35- DAY FU c D42	Unsc h Visits
Study Procedures	-1 (-3)	Prior to Tx		Phone/ On-site c	± 3 days		Phone/ On- site c	

Abbreviations: applic. = applicable; BL = Baseline; D = day; eCRF = electronic case report Form; EOT = end of treatment; FU = Follow-up; ID = identification; PE = physical exam; PK = pharmacokinetic; Screen = Screening; TOC = test of cure; Tx = treatment; Unsch. = unscheduled.

- a. Screening and Baseline/ Day 1 can occur on the same day.
- b. The 25-Day FU visit will occur on study Day 32 (i.e., 32 days after the first dose of study drug and 25 days after EOT).
- c. The 35-Day FU visit will occur on study Day 42 (i.e., 42 days after the first dose of study drug and 35 days after EOT). This will be a telephone call and only a full on-site visit if the subject is symptomatic.
- d. Vaginal examination and samples for mycological testing to be done if the subject is still symptomatic.

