### 7.2.1 Overall Secondary Endpoints

The overall secondary endpoints listed below apply to all eligible fungal diseases:

- The percentage of subjects who achieve Global Response at additional time points as applicable for each disease, disease category and reason for enrollment ([Table 5](#)), as determined by the DRC and by the Investigator
- The percentage of subjects who achieve Clinical Response by pathogen at time points applicable for each disease, disease category and reason for enrollment ([Table 5](#)), as determined by the DRC and the Investigator
- The percentage of subjects who achieve Mycological Response by pathogen at time points applicable for each disease, disease category and reason for enrollment ([Table 5](#)), as determined by the DRC and the Investigator
- The percentage of subjects who achieve Clinical Response by fungal disease, disease category and reason for enrollment at time points applicable for each disease ([Table 5](#)), as determined by the DRC and the Investigator

- The percentage of subjects who achieve Mycological Response by fungal disease, disease category and reason for enrollment at time points applicable for each disease ([Table 5](#)), as determined by the DRC and the Investigator
- The percentage of subjects with a recurrence of the baseline fungal disease at the 25-Day FU for VVC and at the 6-Week FU for all other diseases as determined by the DRC
- ACM at Day 30 (IC and candidemia) and Day 42 for all diseases
- Time to death from any cause
- Describe ibrexafungerp plasma concentrations

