**Mycological Response (Protocol Amendments 2 and 3 aligned with MSG-EORTC outcome response definitions):**

1. Eradication (eradication of the original causative organism cultured or identified by histology/cytology at Baseline)
2. Presumed eradication (missing documentation of the eradication of the original causative organism at Baseline plus resolution of all or some clinical symptoms and physical findings of fungal disease present at Baseline and/or of those that appeared at a subsequent visit)
3. Persistence (persistence of the original causative organism cultured or identified by histology/cytology at Baseline or emergence of a new causative organism)
4. Presumed persistence (missing documentation of the persistence of the original causative organism at Baseline plus no resolution or worsening of any clinical symptoms and physical findings of fungal disease present at Baseline and/or of those that appeared at a subsequent visit)
5. No mycological follow-up results available, for whatever reason (no diagnostic test done at any time point)
6. No mycological evidence at Screening (up to Day 7) (any negative diagnostic test(s) obtained or not done at Baseline [from Screening up to Day 7, inclusive])

Mycological response will be confirmed by the DRC and will include central laboratory results. Reporting of mycological response by PI used different definitions for subjects enrolled under final protocol and subsequent amendments. Complete and partial response were mapped as successful mycological response for subjects under final protocol: Eradication and presumed eradication were mapped as successful mycological response for subjects enrolled under subsequent amendments. The DRC adjudicated mycological responses used the same definition for all subjects as included in the latest amendment.

If relevant mycology findings occur after successful mycological response (proven or presumed eradication), an evaluation will be made as to whether the infection is recurrent (same species as at Baseline) or emergent (different species compared with Baseline). Subjects with recurrent or emergent infection will be classified as mycological failure from the visit onwards where positive cultures were reported, i.e. positive cultures before the FU Visit will be categorized as mycological failure and overall non-successful response on the primary efficacy assessment.

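### VVC response is an endpoint at Day 42, but only symptomatic subjects are scheduled for examination and culture then, so Clinical Cure is out of reach for those scored and well subjects have no score

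*SAP*

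**What the plan says.** **Time points.** The VVC row of SAP Table 5 lists "Day 17, 25-Day FU [Day 32], 35-Day FU [Day 42", and protocol Table 16 lists the same three days. SAP 7.2.1 makes them operative: "The percentage of subjects who achieve Clinical Response by fungal disease, disease category and reason for enrollment at time points applicable for each disease". Parallel items there cover Global and Mycological Response.

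**Definitions (SAP Table 5, VVC).**
- Global Response is "defined as at least 50% reduction from baseline in total composite score, without use of additional antifungal".
- Clinical Response is "Clinical Cure, defined as complete resolution of all signs and symptoms (VSS = 0) without use of additional antifungal", or alternatively VSS < 3.
- Mycological Response is eradication or presumed eradication. Protocol Table 16 lists eradication only.
- The Responder outcome requires both Clinical Cure and eradication.

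**The score.** Protocol Appendix D has six items, each 0 to 3. Burning, itching and irritation are rated by the subject. The three signs are "To be rated by the Investigator during the vulvovaginal examination".

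**What happens at Day 42.** Footnote c of SAP Table 4 says of this visit: "This will be a telephone call and only a full on-site visit if the subject is symptomatic". Footnote d ties examination and sampling to symptoms. Protocol 14.2.1 does the same for the examination, and protocol 14.2.2.1 for culture: "For symptomatic subjects, samples will also be collected at the 35-Day FU visit". The efficacy-assessment row is nevertheless marked at Day 42 without any condition.

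**Missing outcomes.** Under SAP 3.3 and 7.1.1, an outcome deemed neither success nor failure is unknown or not evaluable.

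**The concern.** Whether the Day 42 outcome is measured depends on the outcome itself. The subjects who are doing well have no sign ratings and no culture; those who are examined are there because they have symptoms. A reader would take a Day 42 response rate as evidence of durability after test of cure. As planned, it would mainly reflect how telephone contacts are classified, and that would be settled during programming or adjudication, with the data in hand.

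Mycology leans the other way. SAP 7.2.3 defines "Presumed eradication (missing documentation of the eradication of the original causative organism at Baseline plus resolution of all or some clinical symptoms" (and physical findings), a description that an uncultured, symptom-free telephone contact can fit.

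**Working it through.** The plan gives no figure on this point and no VVC sample size, so there is nothing to reproduce. The check sets the schedule against the definitions.

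**1. Who is scheduled for a complete score and a culture** (protocol 14.2.1, 14.2.2.1 and Table 15; SAP Table 4)

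| Visit | Examination | Culture |
|---|---|---|
| Day 17 (TOC) | all VVC subjects | all VVC subjects |
| Day 32 (25-Day FU) | all VVC subjects | all VVC subjects |
| Day 42 (35-Day FU) | symptomatic only | symptomatic only |

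**2. What an examined Day 42 subject can score**

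VSS = signs (0 to 9) + symptoms (0 to 9).
- All item patterns: 4^6 = 4096. With no symptom: 4^3 = 64. With at least one: 4096 − 64 = 4032.
- With at least one symptom, VSS ≥ 1. None of the 4032 patterns totals 0, so Clinical Cure and the Responder outcome are unreachable.
- VSS < 3 is reachable. A total of 1 arises in 3 symptomatic patterns. A total of 2 arises in 21 patterns overall, 6 of them signs only, leaving 15. So 3 + 15 = 18.
- A 50% fall is reachable. Entry requires VSS ≥ 4 (protocol Table 5). From a baseline of 4, totals of 1 or 2 qualify; from 10, totals of 1 to 5.
- In the 64 symptom-free patterns the total could be 0 to 9, but the signs are not rated, so it is not observed.

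**3. Illustration (assumed: 50 VVC subjects, 40 symptom-free at Day 42)**
- Complete VSS: 50 − 40 = 10 subjects.
- Clinical Cure: 0/10 of those scored, and 0/50 in ITT with 40 not evaluable. If every telephone contact were deemed cured: 40/50 = 80%.
- Mycology: telephone contacts contribute at most 40/50 = 80% as presumed eradications. If k of the 40 are classed as failures because of a positive culture at a previous visit, the contribution is (40 − k)/50; k = 5 (assumed) gives 35/50 = 70%.

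**4. Range (assumed: 100 subjects, share a = 50% to 90% asymptomatic, share q = 80% to 100% of those sign-free)**

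| Quantity | Formula | Result |
|---|---|---|
| Truly cured | 100 × a × q | 40 to 90 |
| Complete VSS | 100 × (1 − a) | 50 down to 10 |
| Cure observed from a complete VSS | – | 0 |
| Cure if telephone contacts count | 100 × a | 50 to 90 |

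**The case against.** **The zero is narrow.** A reader might infer that no VVC response can occur at Day 42. The definitions do not support that: VSS < 3 and a 50% fall remain possible in examined subjects. Symptomatic is also undefined, so a subject whose only complaint lies outside the three rated items could be examined and score 0. Both points stand, which is why the zero is limited to Clinical Cure and the Responder outcome under a stated reading.

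**Mycology is not simply symptom status.** A reader might infer that at least 80% respond in the illustration. SAP 7.2.3 rules this out: after a successful response, recurrent or emergent infection is classed as failure from the visit with the positive culture onwards. A symptom-free subject who turns culture-positive at Day 32 is thus a failure at Day 42. Documented persistence at Days 17 and 32 also fits poorly with missing documentation, and the DRC confirms mycological response using central laboratory results. So 40/50 is a ceiling for telephone contacts, not a floor.

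**A rule may exist elsewhere.** DRC criteria are to be detailed in a Charter that is not among these documents, and the efficacy assessment at Day 42 is unconditional. SAP 2.3 says only that the visit may be a telephone contact. A Charter rule could settle the DRC's classification, but it could not supply sign ratings or cultures that were never scheduled.

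**The stakes are limited.** Recurrence in VVC is assessed at Day 32, when examination and culture are scheduled for all, and the study is exploratory. This stands and limits the weight of the point.

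**Conclusion.** The plan lists composite VVC endpoints at a visit where their components are scheduled only for subjects selected on the outcome. Following it as written leaves Clinical Cure and Responder unobservable from a complete Day 42 VSS. Global Response and VSS < 3 are estimated only in a group biased toward failure. Most well subjects would be not evaluable unless deemed successes under an unstated rule. Under the assumed shares, Day 42 cure could be reported as 0% or as 50% to 90%, depending on that rule.

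This rests on three assumptions: symptomatic means at least one of the three rated symptoms, the examination follows the schedule, and a score means all six items. The percentages are illustrative; the documents give no VVC numbers.

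The point should be corrected, but it concerns one late secondary time point in one disease. It does not reach the Day 17 primary endpoint or the Day 32 assessments.

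**What to change.** - In SAP Table 5, with the matching change to protocol Table 16, remove Day 42 as a time point for VVC Global, Clinical and Mycological Response and for the Responder outcome.
- Name Day 32 as the follow-up time point for these endpoints and for symptom resolution at follow-up. SAP Table 7 does not say which of the two VVC follow-ups is meant.
- At Day 42, report what the plan collects in everyone: symptomatic or not (this decides telephone or on-site visit), other antifungal use (recorded through the 35-Day FU under SAP 6.1) and survival status. Report symptom item scores only if they were in fact recorded by telephone. No section says so, and the VVC diary is collected at TOC.
- If Day 42 is kept, the minimum is an SAP rule stating how asymptomatic telephone contacts are classified for each endpoint and in which denominator.

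Cost: SAP and table-shell wording plus the matching protocol change. No visit or test is added. The composite endpoints lose one late VVC time point.

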	For VVC: TOC (Day 17) (Day 17, 25-Day FU [Day 32], 35-Day FU [Day 42])	For VVC: Global Response = Clinical Success , defined as at least 50% reduction from baseline in total composite score, without use of additional antifungal	For VVC: Global Response (as defined) Clinical Response = Clinical Cure , defined as complete resolution of all signs and symptoms (VSS = 0) without use of additional antifungal (Reference FDA guidelines 2016); Resolved VVC infection (score <3) Mycological Response = mycological eradication for the baseline pathogen Symptom resolution at FU (clinical cure, resolved infection, clinical success) Responder outcome (Clinical Cure and mycological eradication) at TOC and FU

Fungal disease	Primary time point (Secondary time points)	Primary Outcome Definition	Secondary Outcome Definitions (disease-specific outcome definitions, if not previously defined) ^{a, c}
Disseminated/invasive dimorphic fungi: • Coccidioidomycosis • Histoplasmosis • Blastomycosis	EOT (EOT, Day 42, Day 84, 6-Week FU)	Global Response = Global Response based on MSG-EORTC outcome response definitions ^b	Global Response (as defined) Clinical Response (including radiological outcome) and Mycological Response = Clinical and Mycological Responses based on MSG-EORTC outcome response definitions ^b

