5. No mycological follow-up results available, for whatever reason (no diagnostic test done at any time point)
6. No mycological evidence at Screening (up to Day 7) (any negative diagnostic test(s) obtained or not done at Baseline [from Screening up to Day 7, inclusive])

Mycological response will be confirmed by the DRC and will include central laboratory results.

If relevant mycology findings occur after successful mycological response (proven or presumed eradication), an evaluation will be made as to whether the infection is recurrent (same species as at Baseline) or emergent (different species compared with Baseline). Subjects with recurrent or emergent infection will be classified as mycological failure from the visit onwards where positive cultures were reported, i.e. positive cultures before the FU Visit will be categorized as mycological failure and overall non-successful response on the primary efficacy assessment.

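### In SAP Table 5 the VVC Clinical Response reduces to VSS <3 whether or not another antifungal was given, and Mycological Response pools documented with presumed eradication, on which the protocol disagrees with itself

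*SAP*

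**What the plan says.** **Clinical Response, VVC.** Protocol Table 16 opens with "Clinical Response = Clinical Cure". It then runs on in one cell: "complete resolution of all signs and symptoms (VSS = 0) without use of additional antifungal (Reference FDA guidelines 2016); Resolved VVC infection (score <3"). A semicolon separates the two items. Nothing says whether the second is another way to be a Clinical Responder or a separate outcome, and only the first carries the antifungal condition. SAP Table 5 sets the items out as two bullets joined by OR. The first is "Clinical Cure, defined as complete resolution of all signs and symptoms (VSS = 0) without use of additional antifungal (Reference FDA guidelines 2016"); the second is resolved infection, VSS <3, again without an antifungal condition.

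**Mycological Response, VVC.** Protocol Table 16 gives only "mycological eradication for the baseline pathogen". SAP Table 5 adds a second route, "Presumed eradication of the baseline pathogen". SAP 7.2.3 defines that category: "Presumed eradication (missing documentation of the eradication of the original causative organism at Baseline plus resolution of all or some clinical symptoms" and findings. Protocol 18.4.5, the Investigator's assessment, has the same category, not limited by disease, and refers to "successful mycological response (proven or presumed eradication").

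**Unchanged parts.** In both documents the primary VVC Global Response needs at least a 50% fall in total score and no additional antifungal. The named composite also keeps its components; in the protocol it is "Responder outcome (Clinical Cure and mycological eradication) at TOC and FU".

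**The concern.** A definition in which one of two limbs can never decide a case is a drafting fault on any reading. Here the limb that drops out is the one that carries the word cure and excludes subjects given another antifungal. The SAP row then contradicts itself: the primary outcome treats additional antifungal use as failure, while the secondary outcome beside it ignores such use.

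On mycology, a subject whose eradication was never documented can be a success because symptoms improved. For such subjects the endpoint measures symptoms, not mycology. SAP 7.2.1 reports Clinical and Mycological Response by both the Data Review Committee (DRC) and the Investigator, and points to Table 5 for the time points, so the row serves both assessors. Each wider limb can only add responders.

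**Working it through.** The plan has no figure to reproduce here: protocol 18.1 states that no formal sample-size calculation was made, and neither document gives a VVC sample size or target rate.

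**Inputs**
- VSS range 0 to 18: six items scored 0 to 3 (protocol Appendix D).
- VVC entry score of 4 or more (protocol Table 5).
- VVC secondary time points Day 17, Day 32 and Day 42 (protocol Table 16, SAP Table 5).
- Cultures scheduled for all VVC subjects at Day 17 and Day 32, but at Day 42 only if symptomatic (protocol 14.2.2.1, Table 15).
- Illustration only: 52% clinical cure and 63% eradication by Day 10 in the Phase 2b VVC study (protocol 7.1).

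**Step 1: what the OR does.** Write R for use of another antifungal. The SAP rule is (VSS = 0 and not R) OR (VSS <3). Every state in the first bracket is also in the second, so the rule equals VSS <3.

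| VSS | Another antifungal | Cure only | SAP Clinical Response |
|---|---|---|---|
| 0 | no | yes | yes |
| 0 | yes | no | yes |
| 1 or 2 | no | no | yes |
| 1 or 2 | yes | no | yes |
| 3 or more | either | no | no |

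Checking every baseline from 4 to 18, every later score from 0 to 18, and R yes or no gave no exception.

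**Step 2: against Global Response.** The least favourable case is baseline 4 and later score 2: (4 − 2)/4 = 50%, which still meets the threshold. So anyone with VSS <3 and no other antifungal is also a Global success. The only SAP Clinical Responders who fail Global Response are those given another antifungal.

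**Step 3: size, clinical.** One subject moves the rate by 100/n: 10 points at n = 10, 5 at n = 20, 2.5 at n = 40 (all assumed). At n = 20, start from 0.52 × 20 ≈ 10 responders: 10/20 = 50% (Clopper-Pearson 95% CI 27.2 to 72.8). Two reclassified subjects give 12/20 = 60% (36.1 to 80.9).

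**Step 4: size, mycological.** Let m be the share without a culture and s the share of those with some symptom resolution. Assume 63% eradication where cultured, m from 5% to 20%, s from 70% to 100%.
- Uncultured subjects kept in the denominator: documented only = 0.63(1 − m); with presumed = 0.63(1 − m) + ms; difference = ms. Range 0.05 × 0.70 = 3.5 points to 0.20 × 1.00 = 20 points.
- Uncultured subjects left out of the documented-only rate: that rate is 63%, and the difference is m(s − 0.63). Range 0.05 × 0.07 = 0.35 points to 0.20 × 0.37 = 7.4 points.

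The missing-outcome rules (protocol 18.4.3, SAP 3.3) class such subjects as unknown or not evaluable but do not say which denominator applies.

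**The case against.** The strongest reply is that the SAP did not invent either element, and that stands.

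- **Departure from the protocol.** A reader might infer that the SAP overrides the protocol. The documents do not support that as a general statement. Resolved infection with no antifungal condition already sits in the protocol's Clinical Response cell, and OR is one plausible reading of the semicolon. Presumed eradication already counts as success in protocol 18.4.5. The SAP departs from the VVC row of Table 16 on mycology, but not from the protocol as a whole.
- **Responders.** A reader might infer that subjects given another antifungal, or never cultured, enter the named Responder outcome. They do not on the text: it still needs cure and eradication (SAP Table 7). Nor is a missing culture enough by itself; some symptom resolution is also required.
- **Safeguards.** Cure, resolved infection and clinical success are already listed separately under symptom resolution at follow-up. The Myco-ITT population requires the necessary tests, so the mycology effect falls mainly in ITT and PP.
- **Change log.** SAP version 1.1 lists its Table 5 edits as clarification. Version 1.0 is not supplied, so one cannot say which words were new.

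The reply does not rescue the definition. The redundancy holds whatever its origin. The separate symptom listing applies at follow-up, not to Clinical Response at Day 17. Protocol 18.4.2 rests efficacy outcomes on Tables 16 and 17 and points to 18.4.5 for the Investigator's criteria, so 18.4.5 does not settle the DRC's rule. SAP 7.2.3 says the DRC used the latest amendment's definition, but that amendment contains both texts. The DRC Charter might settle it; it is not among the documents.

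**Conclusion.** The point holds for VVC secondary endpoints only. Read literally, SAP Clinical Response is VSS 0 to 2 regardless of other antifungal use, and it disagrees with Global Response for exactly the subjects given another antifungal. The gap is inherited from an ambiguous protocol cell, which the SAP settles on the lenient side. Mycological Response pools documented and presumed eradication, and here protocol Table 16 and protocol 18.4.5 conflict.

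The clinical effect is upward, by 10, 5 or 2.5 points per reclassified subject at an assumed 10, 20 or 40 VVC subjects. How many subjects would be reclassified is unknown. The mycological effect depends on the assumed missing-culture rate and on the denominator: 3.5 to 20 points if uncultured subjects stay in, 0.35 to 7.4 if they are left out of the documented-only rate. The second range would vanish or reverse if symptom resolution among them were at or below 63%. The primary Global Response and the named Responder outcome are untouched. In an exploratory single-arm study this warrants a wording correction; it does not threaten the main result.

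**What to change.** In the VVC row of SAP Table 5:

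1. Apply the no-additional-antifungal condition to the VSS <3 limb as well as to cure. Clinical Response then covers VSS 0 to 2 without another antifungal, and every Clinical Responder is also a Global success.
2. Report Clinical Cure (VSS = 0) and resolved infection (VSS <3) as separate rows at each time point. Cure stays nested inside VSS <3 even after step 1, so a single combined rate would still hide it.
3. Tabulate documented and presumed eradication separately at Day 17 and Day 32. At Day 42, show asymptomatic subjects without a culture as their own category. A culture-only rule there would leave the rate resting on symptomatic subjects, because the others are not cultured by design.
4. State which mycological definition the DRC used for VVC, and which denominator holds subjects without a culture.
5. Reconcile protocol Table 16 with protocol 18.4.5, and record any remaining departure from Table 16 as a change with its reason.

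The cost is SAP wording and a few table rows. The reported VVC secondary rates may be lower.
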